## 4.2 Dose Limiting Toxicity

For the purpose of guiding dose escalation decisions, dose-limiting toxicities (DLTs) are defined by drug-related AEs that occur up to Cycle 1 Day 42. The severity of AEs will be graded according to the National Cancer Institute Common Terminology Criteria for Adverse Events v 4.03 (NCI CTCAE v 4.03). Dose-limiting toxicities will be defined separately for hematologic, non-hematologic, and hepatic non-hematologic events.

In general, for patients who experience an AE that may meet the criteria for a DLT, subsequent administration of the study drugs should be held pending management and/or resolution of the event and assessment of attribution to the study drug. Criteria for subsequent continuation of therapy are outlined in are outlined below.

Dose limiting toxicities are defined separately for hematologic and non-hematologic events as described below.

### 4.2.1 Hematologic Dose Limiting Toxicity

Hematologic DLT is defined as follows:

- Grade 4 neutropenia lasting > 5 days
- $\geq$  Grade 3 febrile neutropenia lasting > 48 hours or any  $\geq$  Grade 3 febrile neutropenia associated with hemodynamic compromise or objective evidence of infection
- Grade 4 thrombocytopenia, irrespective of duration
- Grade 3 thrombocytopenia associated with clinically significant bleeding
- $\geq$  Grade 3 hemolysis
- $\geq$  Grade 3 anemia associated with other clinically significant complications.

The following event will be specifically **excluded** from the definition of hematologic DLT:

- $\geq$  Grade 3 lymphopenia

## 4.2.2 Non-hematologic Dose-Limiting Toxicity

Non-hematologic DLT is defined as any  $\geq$  Grade 3 non-hematologic event **with the following exceptions**:

- Grade 3 electrolyte abnormality that lasts less than 72 hours, is not otherwise associated with clinical complications, and responds to medical intervention
- Grade 3 fever that lasts  $<$  72 hours and is not associated with hemodynamic compromise
- Grade 3 nausea or vomiting that lasts  $<$  72 hours and responds to medical intervention
- Grade 3 or 4 amylase and/or lipase elevation that is not associated with either clinical or radiographic evidence suggestive of pancreatitis
- Grade 3 gastrointestinal AEs of diarrhea, constipation, abdominal pain, cramping, dyspepsia, or dysphagia that resolves to  $\leq$  Grade 1 within 7 days with medical therapy
- Grade 3 fatigue that lasts  $<$  7 days.
- Grade 3 infusion-related reaction or cytokine release syndrome that lasts  $<$  12 hours and responds to medical intervention.
- Grade 3 or 4 endocrinopathy that is adequately controlled with hormone supplementation
- Grade 3 skin toxicity that resolves to  $\leq$  Grade 2 within 14 days of initiation of oral corticosteroids
- Grade 3 inflammatory reaction (e.g., with associated pain, swelling) attributed to a local anti-tumor response (e.g., inflammatory reaction at sites of metastatic disease, lymph nodes, etc.) that resolves to  $\leq$  Grade 2 within 7 days.

Note: The following Grade 2 or greater non-hematologic AE may also be considered as DLT:

- Grade 2 AEs that are prolonged inordinately, based upon the medical judgment of the Investigator, and/or lead to permanent discontinuation of MGA012 due to patient intolerance.
- Eye pain or reduction in visual acuity that does not respond to topical therapy and does not improve to Grade 1 within 14 days of the initiation of topical therapy, or that requires systemic treatment.

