**Table 1 Overall Summary of Number of Patients with Adverse Events by Preferred Term of Diarrhea**

Patients Reporting at Least One event of Diarrhea (PT)	QW- 0.8 µg/kg (N=10)	QW Other (0.6, 1 µg /kg) (N=11)	Q3W- 1 µg/kg (N=28)	Q3W Other (0.6, 1.5, 3 µg /kg) (N=14)	BiW (0.5 µg /kg) (N=6)	LID (0.5/1 µg /kg) (N=6)	All (N=75)
Diarrhea	7 (70.0%)	10 (90.9%)	27 (96.4%)	13 (92.9%)	2 (33.3%)	5 (83.3%)	64 (85.3%)
Treatment-Related Diarrhea a	7 (70.0%)	10 (90.9%)	26 (92.9%)	13 (92.9%)	2 (33.3%)	5 (83.3%)	63 (84.0%)
Diarrhea ≥ Grade 3 a	1 (10.0%)	2 (18.2%)	10 (35.7%)	7 (50.0%)	1 (16.7%)	2 (33.3%)	23 (30.7%)
Treatment-Related Diarrhea ≥ Grade 3 a	1 (10.0%)	2 (18.2%)	10 (35.7%)	7 (50.0%)	1 (16.7%)	2 (33.3%)	23 (30.7%)
Serious Diarrhea	1 (10.0%)	2 (18.2%)	10 (35.7%)	5 (35.7%)	1 (16.7%)	3 (50.0%)	22 (29.3%)
Treatment-Related Diarrhea	1 (10.0%)	2 (18.2%)	10 (35.7%)	5 (35.7%)	1 (16.7%)	3 (50.0%)	22 (29.3%)
Diarrhea that Resulted in Study Discontinuation	0	0	0	3 (21.4%)	0	0	3 (4.0%)
Diarrhea that Resulted in Drug Withdrawal	0	0	0	3 (21.4%)	0	0	3 (4.0%)
Diarrhea Adverse Events of Special Interest	0	2 (18.2%)	9 (32.1%)	6 (42.9%)	0	2 (33.3%)	19 (25.3%)

a Includes events with causality assessments of 'Possible', 'Probable' or 'Definite'.

b Based on CTCAE criteria version 4.0

Data cut on 10 January 2018

Abbreviations: BiW = twice a week; QW = once a week; Q3W = every three weeks; LID= Lead-in Dose.

Finally, among 59 response-evaluable patients, as of the cut-off date of 10 January 2018, 19 patients had stable disease (SD), 4 patients on the QW schedules, 14 patients on the Q3W schedule, and 1 patient on the LID schedule (see [Table 2](#)). Among these patients, 7 patients had SD for at least 12 weeks from first dose of MGD007. One patient who is now off study, who was treated at the 1.5 µg/kg dose of MGD007, a dose level that exceeds the MTD, sustained a confirmed partial response and remained on treatment for 8 months since initiation of therapy. Additionally, a patient treated at the 1.0 µg/kg dose of MGD007 sustained an unconfirmed partial response and had been on treatment for more than 4 months. In addition to the clinical evidence of antitumor activity, IHC analyses of fresh tumor biopsy samples obtained from patients following treatment at 1.0 µg/kg in the Tumor Biopsy Cohort revealed on-target binding of MGD007 to gpA33 on cancer cells.

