## 2.6 MGD007/MGA012 Combination Dose Selection

In this study, only the dose for MGD007 will be escalated; the dose for MGA012 will be kept constant at the dose of 3 mg/kg. The initial dose proposed for MGD007 in this study is 0.4 µg/kg QW (QW Cohort). The rationale for selection of the respective doses of MGD007 and MGA012 is described below.

MGD007 will be given QW as 120-minute infusion, with planned escalations from 0.4 to 0.8 µg/kg combined with a 3 mg/kg dose of MGA012 IV (60-minute infusion) given on a Q2W schedule. In the event that a given dose level is found to exceed the MTD, subsequent patients will be dosed at the next lowest dose level, or an intermediate dose level designated based on review of the existing data, and consultation between the study investigators and the Sponsor.

On days when both MGD007 and MGA012 will be administered, MGA012 will be administered first.

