#### 4.1.1 Dose Escalation Phase

The goal of the Dose Escalation Phase is to initially characterize the safety and tolerability of MGD007 combined with MGA012, and to define the DLTs and MTD (or MAD if no MTD is defined) of the combination. The MTD is defined as the dose level at which  $< 33\%$  of patients experience a DLT.

For the purpose of guiding decisions regarding dose escalation, the definition of DLT will be based on the occurrence of drug-related AEs that occur up to Cycle 1 Day 42 of MGD007 combined with MGA012 administration.

Dose escalation will follow a conventional 3+3+3 design: MGD007 and MGA012 will be evaluated in sequential escalating doses in cohorts of 3 to 9 patients each. Dose levels of MGD007 to be evaluated are displayed in **Table 8**.

MGA012 will be administered at an unchanged dose of 3 mg/kg Q2W, i.e., the recommended dose in combination, beginning on Cycle 1 Day 15. On days when both MGD007 and MGA012 will be administered, MGA012 should be administered first.

During the 42-day DLT evaluation period, patients who receive less than 75% of the planned doses of either MGD007 or MGA012 secondary to AEs considered unrelated to study treatment or any other cause unrelated to study treatment are considered unevaluable for safety and toxicity during the DLT evaluation period and will be replaced.

Continued dose escalation will proceed using a conventional 3+3+3 design according to the dose escalation rules outlined below. Dose escalation cohorts are presented in **Table 8**.

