### **5.3 Withdrawal of Patient from the Study**

Patients who withdraw before Cycle 1 Day 42 during the Dose Escalation Phase for a reason unrelated to drug toxicity or efficacy may be considered to have inadequate data to support efficacy assessment (see [Section 4.1.1](#)). In this case, replacement patients may be enrolled but the patients will be considered in intention to treat. These patients will be followed for safety assessments (see [Section 12.2](#)).

See [Section 4.5.1](#) for replacement criteria for those patients who were planned to have paired tumor biopsies.

Procedures for handling patients who fail to appear for study visits and criteria regarding when to consider patients lost-to-follow-up (LTFU) will be defined in the Study Procedures

Manual. A patient may be determined to be LTFU after there have been 3 documented phone contact attempts. If this fails, a certified letter should be sent to the patient. Only after these attempts have failed can a patient be determined to be LTFU.

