## 5.4 Rules for Study Treatment Discontinuation

Patients who tolerate treatment may continue to receive treatment with the study drug(s) as specified in the protocol until any one of the following conditions are met:

- Patient meets any criteria for immune-related disease progression (irPD)
- Withdrawal of patient due to an AE or SAE
- Withdrawal of patient consent
- Completion of protocol-defined therapy
- Investigator discretion
- Pregnancy
- Occurrence of drug-related DLT
- Dose delay > 28 days due to drug-related AE
- Repeated administration of prohibited concomitant medications
- The Sponsor, Investigator, or Regulatory Agency terminates the study
- Death

For individual patients who meet these criteria, but who are otherwise considered to be experiencing compelling clinical benefit in the judgment of the Investigator, consideration may be given to continue treatment with the MGD007 and MGA012 combination, for up to maximum of total of 12 cycles, on a case-by-case basis, in consultation with the Sponsor.

For patients who experience drug-related DLTs that occurs prior to the initiation of MGA012, or for selected immune-related adverse events clearly related to the mechanism of action of MGA012, continued treatment of patients with either MGA012 or MGD007 monotherapy, respectively, may be considered selectively on a case-by-case basis, in consultation with the Sponsor.

If the Investigator decides that the patient should be withdrawn from the study or from dosing for any reason other than disease progression, the site must enter the information in the eCRFs within 24 hours ([Section 12.2.2](#)).

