## **14.7 Safety Endpoints and Analyses**

### **14.7.1 Adverse Events**

Only treatment-emergent AEs will be summarized in tables. The following AEs will be provided in summary tables as well as displayed in listings:

- All AEs
- AEs with CTCAE severity grade  $\geq 3$
- Study drug related AEs
- Study drug related AEs with CTCAE severity grade  $\geq 3$
- SAEs
- Study drug related SAEs
- AEs that result in discontinuation of study treatment
- AEs that led to interruption or withdrawal of individual study drug
- Fatal AEs
- Immediately reportable AEs (if applicable)
- AEs of special interest (if applicable)

All of these tables will display the number and percent of patients that experience the given event and will display events by MedDRA System Organ Class (SOC) and Preferred Term (PT). Events will be displayed alphabetically for SOC and in descending order of overall PT incidence. An overall summary of AEs will display the number and percent of patients who experience at least one event of each of the above types.

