Vital Signs: Temperature, heart rate, blood pressure, and respiratory rate. Screening: Vital signs will be taken once. Cycle 1 Days 1, 8, 22, 36, and 50 (MGD007 alone): Vital signs will be taken immediately before the infusion (up to 10 minutes before the infusion); at 15 (± 5 min), 30 (± 5 min), and 60 minutes (± 10 min) after the start of the infusion; at the end of infusion (± 10 min); and at 1- and 4-hours after completion of the infusion (±10 min). The 4-hour post infusion vital signs may be deferred based on the judgment of the investigator for all days except Cycle 1 Day 1 Cycle 1 Days 15, 29, 43 (MGA012 and MGD007 combined): Vital signs will be taken immediately before MGA012 infusion (up to 10 minutes before the infusion) and at the end of MGA012 infusion (±10 min); at 15 (± 5 min), 30 (± 5 min), and 60 minutes (± 10 min) after the start of MGD007 infusion; at the end of MGD007 infusion (± 10 min); and at 1- and 4-hours after completion of MGD007 infusion (±10 min). The 4-hour post infusion vital signs may be deferred based on the judgment of the investigator for all days except Cycle 1 Day 15. Cycle 2 and Beyond (MGA012 and MGD007 combined): Vital signs will be taken immediately before MGA012 infusion (up to 10 minutes before the infusion) and at end of MGA012 infusion (±10 min); at the end of the MGD007 infusion (± 10 min); and at 1 hour after completion of the infusion (±10 min). Cycle 2 and Beyond (MGD007 alone): Vital signs will be taken immediately before MGD007 infusion (up to 10 minutes before the infusion); at the end of the MGD007 infusion (± 10 min); and at 1 hour after completion of the infusion (±10 min). At End of Treatment: Visit vital signs will be taken once.																	
Hematology	X	X		X	X		X			X		X	X	X		X	
See Appendix 2 for list of hematology assessments; To be taken pre-infusion. Labs can be taken up to 3 days before infusion.																	
Serum Chemistry	X	X		X	X		X			X		X	X	X		X	
See Appendix 2 for list of chemistries; To be taken pre-infusion. Labs can be taken up to 3 days before infusion.																	
Coagulation	X	X		X	X		X			X		X	X	X		X	
See Appendix 2 for list of coagulation assessments; To be taken pre-infusion. Labs can be taken up to 3 days before infusion.																	
Endocrine tests	X									X						X	

QW Cohort																

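### The Grade 2 intolerance route to a DLT names MGA012 only and leaves out MGD007, the one drug being escalated

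*Protocol*

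**What the plan says.** Protocol 4.2.2 makes any non-hematologic event of Grade 3 or higher a DLT, with listed exceptions. A note then gives discretion to count certain Grade 2 AEs. One limb, which names no drug, covers events the Investigator judges inordinately prolonged. The other covers events that "lead to permanent discontinuation of MGA012 due to patient intolerance". The limbs are joined by and/or.

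The surrounding rules are:

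- Section 2.6: "In this study, only the dose for MGD007 will be escalated". MGA012 stays at 3 mg/kg and, under 4.1, starts on Cycle 1 Day 15. The DLT window runs to Day 42.
- Section 4.3: the DLT count decides whether the MTD for MGD007 has been exceeded.
- Section 4.1.1: patients receiving under 75% of planned doses "secondary to AEs considered unrelated to study treatment or any other cause unrelated to study treatment are considered unevaluable" and are replaced only if the shortfall has one of those causes.
- Section 5.3: replacement may be made for patients who "withdraw before Cycle 1 Day 42 during the Dose Escalation Phase for a reason unrelated to drug toxicity or efficacy".
- Section 5.4: "Withdrawal of patient due to an AE or SAE" is a reason for stopping treatment.

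The SAP repeats the Day 42 window and adds no DLT criterion.

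**The concern.** Intolerance that ends treatment is informative about dose whatever its grade, which is presumably why the second limb exists. As written, it gives that weight to the fixed-dose drug and withholds it from the drug whose dose is being chosen. The protocol offers no reason for the difference. Elsewhere it does not favor one drug: 12.2.2 makes AEs that permanently end study drug immediately reportable, and 14.7.1 tabulates "AEs that led to interruption or withdrawal of individual study drug".

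The error runs one way. It can only undercount intolerance of MGD007, so it can only make a dose look better tolerated against the 33% MTD criterion.

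**Working it through.** **Which events are left out.** The criteria in 4.2.1 to 4.2.3, applied to a drug-related Grade 2 AE within the window:

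| Situation | Can it be counted? |
|---|---|
| Inordinately prolonged, either drug, from Day 1 | Yes, first limb |
| Both drugs permanently stopped after MGA012 has started | Yes, second limb |
| Early AE that later leads to stopping MGA012 | Yes, second limb |
| Not prolonged; MGD007 stopped, MGA012 not permanently stopped | No |
| Not prolonged; patient withdrawn before Day 15, MGA012 never started | No, on a literal reading |

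**Whether such a patient leaves the denominator.** By Appendix 1, MGD007 doses due by Day 42 fall on Days 1, 8, 15, 22, 29 and 36, which is 6; the first 2 precede any MGA012. The 75% threshold is 0.75 × 6 = 4.5, so 5 doses are needed. A patient who stops after the first dose has had 1/6 = 17%. The shortfall is drug-related, so neither 4.1.1 nor 5.3 applies. The patient stays in the cohort without a DLT.

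**Effect on one cohort under 4.3.** With no other DLT among the first 3 patients, one omitted event gives 0/3 (escalate) instead of 1/3 (enroll 3 more). With one counted DLT, it gives 1/3 (enroll 3 more) instead of 2/3 (MTD exceeded).

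**The plan's own figure.** 3 dose levels × 9 patients = 27, as Protocol 14.1 states. The concern does not touch it.

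**What the documents say about frequency.** There is no rate for this event. The nearest entry in Protocol Table 1 is "Diarrhea that Resulted in Drug Withdrawal": 0/10 at 0.8 µg/kg weekly and 0/11 at the other weekly doses, so 0/21. The exact two-sided 95% upper limit is 1 − 0.025^(1/21) = 0.161, or 16%. This is one preferred term, at any grade, on monotherapy. In the same 21 patients, treatment-related diarrhea occurred in 7 + 10 = 17 and was Grade 3 or higher in 1 + 2 = 3. So 14 had at most Grade 1 or 2; Grade 2 is not shown separately.

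**Illustration with assumed rates.** Let p be the DLT probability per patient, q = 1 − p and a = 3pq². A dose is cleared by 0/3; by 1/3 then 0/3; or by 1/3, 1/3, then 0/3 (2/9 = 22%, below the 4.3 limit of 3 in 9):

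P(clear) = q³(1 + a + a²)

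At p = 0.20: q³ = 0.512, a = 0.384, P = 0.512 × (1 + 0.384 + 0.147) = 0.784. The other cells use the same formula, with omitted events assumed to occur in patients who have no counted DLT, so that the rates add.

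| Counted DLT rate | As written | +1 point counted | +2 points | +5 points |
|---|---|---|---|---|
| 10% | 95% | 94% | 92% | 88% |
| 20% | 78% | 76% | 74% | 67% |
| 30% | 56% | 54% | 52% | 45% |

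Neither the DLT rates nor the added points come from the documents. If no such events occur, there is no effect.

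**The case against.** The strongest reply is that the gap is nearly closed in practice.

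- Sections 5.4 and 7 foresee MGA012 alone, within the window, only after a DLT that preceded MGA012, and that patient is already counted. The switch to MGA012 monotherapy in Appendix 1 comes after two full cycles.
- The permanent-stop instructions in Section 7 generally name both drugs. The single-drug exception, Grade 3 or 4 pneumonitis, names MGA012. None names MGD007 alone.
- In a combination regimen, withdrawal before Day 15 can reasonably be read as ending both drugs.
- The note is permissive, and its first limb rests on Investigator judgment.
- The event would be seen: it is reportable within 24 hours under 12.2.2. Section 4.3 requires review by the Medical Monitor, the Pharmacovigilance Physician and the Investigators before escalation.
- Section 4.1.1 does not say outright that a patient stopped early for toxicity is scored as DLT-free; that follows from the absence of any rule to the contrary.

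Most of this stands, and it is why the point is minor. It does not remove the gap. Section 5.4 lists AE withdrawal as a stopping reason with no grade threshold, and it is doubtful that a drug never started can be permanently discontinued. Visibility and review may protect the decision to escalate, but they do not put the event into the count that defines the MTD. Discretion helps only for events the note lists.

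**Conclusion.** The concern holds. The second limb names only the fixed-dose drug, and no other criterion in Protocol 4.2 or the SAP covers a non-prolonged Grade 2 event that ends MGD007 alone, or ends treatment before Day 15. The Day 15 part depends on reading the phrase literally.

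The gap is narrow and its size cannot be estimated from the documents. At 1 point of omitted events, the chance of clearing a dose is overstated by about 1 to 2 percentage points; at 5 points, by about 7 to 11. Those figures show direction only. This is worth correcting, but it does not threaten the design.

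**What to change.** In the Grade 2 note in Protocol 4.2.2, make the second limb refer to permanent discontinuation of *MGD007 and/or MGA012* because of patient intolerance. This also settles the case of a patient withdrawn before MGA012 begins.

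The cost is one phrase in an amendment. Slightly more events may be counted as DLTs. The planned 27 escalation patients, the total of 27 + 25 = 52 and the visit schedule are unchanged.

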### 4.2.3 Hepatic Non-hematologic Dose Limiting Toxicity

Hepatic non-hematologic DLT will be defined as follows:

- Any elevation of one or more transaminases  $> 8 \times$  the institutional upper limit of normal (ULN) irrespective of duration.
- Any Grade 3 elevation of one or more transaminases  $> 5.0 - 8.0 \times$  the ULN that does not resolve to Grade 2 (i.e.,  $> 3.0 - 5.0 \times$  ULN) within 7 days and Grade 1 (i.e.,  $> \text{ULN} - 3.0 \times$  ULN) within 14 days. In addition, steroids must be tapered to  $\leq 10$  mg of prednisone or equivalent per day, by Day 14.
- A Grade 3 elevation of total bilirubin that is  $> 5 \times$  the ULN, irrespective of duration.
- Any Grade 3 elevation of total bilirubin  $> 3.0 - 5.0 \times$  ULN that does not resolve to Grade 2 (i.e.,  $> 1.5 - 3.0 \times$  ULN) within 7 days and Grade 1 (i.e.,  $> \text{ULN} - 1.5 \times$  ULN) within 14 days. In addition, steroids must be tapered to  $\leq 10$  mg of prednisone or equivalent per day, by Day 14.
- Any event meeting the criteria for Hy's law as follows (all 3 features):
  - Aspartate aminotransferase (AST) and/or alanine aminotransferase (ALT)  $> 3 \times$  ULN
  - Concurrent elevation of total bilirubin  $> 2 \times$  ULN without initial evidence of cholestasis
  - No alternative etiology can be identified

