9. For the 15 patients who will have paired tumor biopsies, tumor lesions must be accessible for biopsy with acceptable clinical risk in the judgment of the investigator. Paired tumor biopsies will be mandatory if tumor lesions are accessible for biopsy with acceptable clinical risk in the judgment of the investigator and after discussion with the Sponsor. Fifteen paired biopsies will be required in each cohort at the end of the Cohort Expansion Phase. For each patient, the identified lesion to be biopsied should not have been previously irradiated and should not be the only lesion being utilized as measurable disease target lesion for objective response assessment. The lesion to be biopsied should be of sufficient size to enable acquisition of at least 2 tumor biopsy cores using a biopsy needle.
10. Acceptable laboratory parameters as follows:
  - a. Platelet count  $\geq 100 \times 10^3$ /microliter without transfusion within 4 weeks prior to the initiation of study drug.
  - b. Hemoglobin  $\geq 8.0$  g/dL without transfusion within 1 week prior to the initiation of study drug.
  - c. White blood cell count (WBC)  $\geq 2.0 \times 10^3$ /microliter in the absence of any growth factor support within 4 weeks prior to the initiation of study drug.
  - d. Absolute neutrophil count  $\geq 1.5 \times 10^3$ /microliter in the absence of any growth factor support within 4 weeks prior to the initiation of study drug.
  - e. ALT/AST  $\leq 3.0$  times the ULN, up to 5.0 times the ULN for patients with liver metastases.
  - f. Total bilirubin  $\leq 1.5$  times ULN, except patients with Gilbert's syndrome, who may enroll if the conjugated bilirubin is within normal limits.
  - g. Creatinine  $< 1.5$  mg/dL, or a calculated or measured creatinine clearance  $> 50$  mL/min.
  - h. Negative urine or serum pregnancy test for women of child-bearing potential.

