## 7.5 Immune-Related Adverse Events

Blockade of immune checkpoints (PD-1, PD-L1 and CTLA-4) has been associated with several immune mediated adverse events that develop as a result of disruption of immune tolerance in normal tissues ([18](#), [36](#), [43](#)). These include but are not limited to pneumonitis, autoimmune hepatitis, glomerulonephritis, central neurotoxicity (encephalitis), peripheral neuromuscular toxicity, diarrhea or colitis (discussed in [Section 7.3](#)), hypophysitis, thyroiditis, or other autoimmune endocrinopathies (e.g., pancreatitis and diabetes), myocarditis, and Stevens Johnson Syndrome/Toxic Epidermal Necrolysis. These IrAEs can occur late and require a prolonged follow up. The occurrence of any of these may dictate interruption and potentially discontinuation of study drug administration pending further evaluation and reporting them to the Sponsor as AESIs. Most low-grade immune-related AEs (irAEs) can be managed symptomatically. Persistent low-grade or moderate toxicities may require treatment with corticosteroids or in refractory cases other immune suppressing agents such as

mycophenolate or infliximab. High-grade immune-related toxicities will, in almost all cases, require treatment with high-dose corticosteroids.

Temporary interruptions of the study drugs may be required in the event of treatment-related, immune-related toxicity. General guidelines for specific toxicity regarding dosing and treatment are provided below. All toxicities will be graded according to NCI CTCAE v4.03.

Patients who receive corticosteroid therapy for  $\geq 4$  weeks at a dose equivalent to  $\geq 20$  mg of prednisone per day, consideration should be given to implementation of antibiotic prophylaxis for opportunistic infections.

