## 7.5.1 Hepatic Toxicity

### 7.5.1.1 Elevations in Transaminases

Treatment management algorithm for patients experiencing hepatic toxicity are as follows:

- Grade 1 elevations - No specific therapy required.
- Grade 2 elevations - For elevations in transaminases 3 to  $5 \times$  ULN, rule out viral and other etiologies, and consider immediate oral steroids such as prednisone 60 mg/day divided twice daily, and hold MGD007 and MGA012.
  - If improvement to  $\leq$  Grade 1 does not occur within 48 hours consider IV steroids such as methylprednisolone at 2 mg/kg/day divided twice daily or oral steroids such as prednisone 60 to 120 mg per day, divided twice daily.
  - Resume MGD007 and MGA012 at the next scheduled dose if no more than 2 doses of the combination were missed.
  - If improvement to  $\leq$  Grade 1 does not occur within 14 days, discontinue MGD007 and MGA012.
- Grade 3 elevations - Hold MGD007 and MGA012.
  - For elevations in transaminases  $> 8 \times$  ULN, permanently discontinue MGD007 and MGA012.
    - Begin immediate IV steroids, and
    - If no response to corticosteroid therapy within 3 to 5 days is observed, consider adding immune suppression therapy with mycophenolate.
    - Monitor liver function tests at least twice weekly (or more frequently as clinically appropriate in the judgment of the Investigator) until transaminases have returned to Grade 1 or baseline.
  - For elevations in transaminases  $> 5$  but  $\leq 8 \times$  ULN:

- Begin immediate IV steroids; suggest methylprednisolone at a dosage of 2 mg/kg/day divided twice daily.
- Consider additional immune suppression as above for patients who do not respond to corticosteroid therapy within 3 to 5 days.
- Monitor liver function tests at least twice weekly (or more frequently as clinically appropriate in the judgment of the Investigator) until transaminases have returned to Grade 1 or baseline.
- If the elevation does not improve to Grade 2 within 7 days and to Grade 1 within 14 days, discontinue MGD007 and MGA012.
- Resume MGD007 and MGA012 administration if following conditions are met:
  - Laboratory elevations downgrade to  $\leq$  Grade 2 within 7 days and improve to  $\leq$  Grade 1 or baseline within 14 days.
  - Steroids have been tapered to  $\leq$  10 mg per day of prednisone or equivalent.
  - On resuming MGD007 and MGA012, AST, ALT, and total and direct bilirubin laboratory test values will be evaluated at least once per week for 3 consecutive weeks.

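### A >5.0–8.0 × ULN transaminase rise that returns fully to baseline still counts as a DLT in liver-metastasis patients who enter above 3.0 × ULN, and Section 7.5.1.1 gives opposite dosing instructions for it

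*Protocol*

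**What the plan says.** **Entry.** Protocol 5.1, criterion 10e, caps ALT/AST at 3.0 × ULN in general, but allows values "up to 5.0 times the ULN for patients with liver metastases".

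**DLT definition.** The second bullet of Protocol 4.2.3 concerns "Any Grade 3 elevation of one or more transaminases" above 5.0 and up to 8.0 × ULN. It is a DLT unless it resolves to Grade 2 (5.0 × ULN or less) within 7 days and to Grade 1 (3.0 × ULN or less) within 14 days. Steroids must also be down to 10 mg/day of prednisone or equivalent by Day 14. Baseline is not mentioned. Under 4.2 the event must be drug-related and occur by Cycle 1 Day 42.

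**Dosing rules for the same band.** Protocol 7.5.1.1 has three relevant Grade 3 instructions:

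- Discontinue: "If the elevation does not improve to Grade 2 within 7 days and to Grade 1 within 14 days, discontinue MGD007 and MGA012".
- Resume: values must be at Grade 2 or better within 7 days and at "Grade 1 or baseline within 14 days", with the steroid taper met.
- Monitor: liver tests continue "until transaminases have returned to Grade 1 or baseline".

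**Baseline.** SAP 6.1 defines it as the last value before the first MGD007 dose.

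**The concern.** The entry criterion deliberately admits patients whose ALT/AST is already Grade 2. The 14-day target in 4.2.3 does not carry that allowance forward. A patient who enters above 3.0 × ULN can have a drug-related rise that reverses completely and still be scored as unrecovered, because recovery is set below where the patient started.

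Two things depend on this. The DLT count drives the escalation decisions in Protocol 4.3, and a drug-related DLT is a reason to stop treatment under 5.4. Separately, a site following 7.5.1.1 finds one bullet telling it to stop both drugs and another allowing it to restart them, on the same laboratory values. Section 4.4.1 sends both escalation and expansion patients to Section 7 for restart rules, so the second problem is not confined to escalation.

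**Working it through.** The plan states no figure to reproduce here. The check compares thresholds and then runs the rules on example courses.

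**Step 1: compare the targets with the permitted baseline.** Let B be baseline ALT/AST in multiples of ULN.

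- The 7-day target is 5.0 and B is at most 5.0 (10e), so this target is never below baseline.
- The 14-day target is 3.0, so it lies below baseline whenever B > 3.0.
- Fall below own baseline needed to reach the 14-day target: 1 − 3.0/B.
- Rise needed to reach the lower edge of the DLT band: 5.0/B.

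| B (× ULN) | Fall below baseline, 1 − 3.0/B | Rise to 5.0 × ULN, 5.0/B |
|---|---|---|
| 3.0 | 0.0% | 1.67-fold |
| 3.5 | 14.3% | 1.43-fold |
| 4.0 | 25.0% | 1.25-fold |
| 4.5 | 33.3% | 1.11-fold |
| 5.0 | 40.0% | 1.00-fold (any rise enters the band) |

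**Step 2: run the rules on two courses.** Both are taken as drug-related, with steroids at 10 mg/day or less by Day 14. The taper has to be assumed, because 7.5.1.1 starts IV steroids at once in this band.

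| | Patient A | Patient B |
|---|---|---|
| Baseline | 4.0 | 2.5 |
| Peak | 6.0 (6.0/4.0 = 1.5-fold) | 6.0 (6.0/2.5 = 2.4-fold) |
| At 7 days | 4.5 (target met) | 4.5 (target met) |
| At 14 days | 4.0 (above 3.0) | 2.5 (at most 3.0) |
| DLT under 4.2.3 | Yes | No |
| 7.5.1.1 discontinue bullet | Applies | Does not apply |
| 7.5.1.1 resume bullet | Met (at baseline) | Met |

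Both patients return exactly to baseline, and A has the smaller relative rise. A is the DLT, and A meets the discontinue and resume conditions together. The same triple result (DLT, discontinue, resume) occurs for baseline 3.5 with 4.5 at 7 days and 3.5 at 14 days, and for baseline 5.0 with 5.0 at both times. With a baseline of 3.0 or less the two bullets agree.

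**Step 3: is this a one-off or the protocol's general approach?** The bilirubin DLT in 4.2.3 has the same structure, but entry bilirubin is capped at 1.5 × ULN (10f), which is the Grade 1 limit used in that DLT. Gilbert's syndrome apart, its 14-day target is not below a permitted baseline. The mismatch therefore appears where the higher liver-metastasis limit applies. Elsewhere the protocol names baseline as an end point of recovery: in the resume and monitoring bullets of 7.5.1.1, and in SAE follow-up in 12.2.3.

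**Step 4: what one such event does under 4.3.** One DLT among the first 3 patients adds 3 patients. If none of those 3 has a DLT, escalation continues. Declaring the MTD exceeded takes at least 2 of 3, 3 of 6 or 3 of 9. A single event of this kind never suffices alone. It needs at least one other DLT in the first 3, or at least two others by 6 or 9 patients.

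**The case against.** The best defence is that fixed ULN limits are a deliberate safety choice. This trial combines a CD3 engager with an anti-PD-1 antibody, and an already abnormal liver is a reason for strictness. That is a fair position and it explains why the error is conservative. It does not explain why 7.5.1.1 lets the same patient resume, and no text presents the lower target as intended for patients admitted under the 10e allowance.

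It can also be said that only drug-related events count (4.2), that the rules in Section 7.5 are introduced as general guidelines, and that 5.4 allows continued treatment case by case. All three are true. A drug-related rise that fully reverses is still counted, and a discretionary continuation does not change the DLT count.

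Three stronger readings are tempting and are not supported.

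- **The Grade 2 rule stops these patients at their entry value.** That rule says to "consider immediate oral steroids such as prednisone 60 mg/day divided twice daily, and hold MGD007 and MGA012", and its stopping clause reads "Grade 1 does not occur within 14 days, discontinue MGD007 and MGA012", with no mention of baseline. However, Section 7.5 sets the context: "Temporary interruptions of the study drugs may be required in the event of treatment-related, immune-related toxicity". Protocol 12.1.1 requires an adverse event to be new or worse than baseline, 9.4 records conditions before the first dose as medical history, and SAP 5.2.1 defines treatment-emergent events in line with this. A stable entry value is not treatment-related toxicity.
- **Such holds would push patients below the 75% dose limit in 4.1.1 and make them unevaluable.** This rests on the reading just rejected. It also ignores 4.4.1, under which treatment resumes at the point of interruption.
- **The wording raises the chance of declaring the MTD exceeded by a stated amount.** Any such figure assumes that the event has already occurred among the first patients and assumes a DLT rate for the others. It would describe any single disputed DLT, not the effect of this wording.

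**Conclusion.** The concern holds in a limited form. For liver-metastasis patients entering above 3.0 and up to 5.0 × ULN, the 14-day transaminase target in 4.2.3 is below their permitted baseline, so a drug-related excursion that reverses fully is scored as a DLT. For the same course, the Grade 3 discontinue and resume bullets of 7.5.1.1 contradict each other. Both conclusions follow from the text alone, given a drug-related event and a completed steroid taper.

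The point is minor. The error errs towards caution, patients at or below 3.0 × ULN are untouched, and one event cannot by itself declare the MTD exceeded. The documents give neither the share of patients entering above 3.0 × ULN nor the rate of such excursions, so no frequency or overall effect on escalation can be stated. The pattern of wording suggests an entry allowance that was not carried through rather than a considered restriction, but that is an inference.

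**What to change.** 1. In the second bullet of 4.2.3, change the 14-day transaminase target to Grade 1, or baseline if baseline ALT/AST was above 3.0 × ULN, with baseline as defined in SAP 6.1. Keep the 7-day target, the steroid-taper condition, the rule for values above 8 × ULN and the Hy's law rule unchanged for everyone.
2. Make the same change in the Grade 3 discontinue bullet of 7.5.1.1, so that it agrees with the resume bullet.

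Optionally, the Grade 2 recovery wording in 7.5.1.1 could accept Grade 1 or baseline for patients who worsen from an elevated baseline. This is a clarification only.

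The cost is wording in two bullets, and baseline values are already collected. The price is a slightly less conservative hepatic DLT in a subgroup of undocumented size. For example, a patient who enters at 5.0 × ULN, peaks at 7.9, and is back at 5.0 at both 7 and 14 days with the taper met would no longer count. A sustained rise still would: entry at 5.0 with values staying at 7.4 fails the 7-day limit of 5.0 and is above baseline at 14 days.
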